9.4.1 Source Documents

Providers are compensated for their time completing data abstraction into the eCRF and subsequent data verification as necessary. No source documents will be provided to [REDACTED] for verification; however, [REDACTED] will require duplicate data entry for a sample of patients (see **Section 9.8.2 Data Validation**) after initial data collection to verify data point accuracy.

9.4.2 Dataset and Records

9.5 STUDY SIZE

The total target number of patients is up to 120 patients, including up to 70 patients with an *NRG1* gene fusion-positive solid tumor treated with afatinib and up to 50 patients with an *NRG1* gene fusion-positive solid tumor who had not received afatinib at the time of data collection. The target number of patients was based on the results of a pilot feasibility study conducted by [REDACTED] with BI.

In December 2019, [REDACTED] conducted outreach to approximately 800 providers in [REDACTED] to inquire as to the number of patients with *NRG1* gene fusion-positive solid tumors treated with afatinib they had personally managed or who were cared for at their practice. Providers were presented with similar inclusion criteria as those described herein. In total, 12 oncologists completed short eCRFs describing a total of 108 patients. Of the 108, 67 patients were treated with afatinib and 41 had not received afatinib therapy.

Based on the feasibility study, [REDACTED] will target number of patients of up to 70 afatinib-treated patients with *NRG1* gene fusion-positive solid tumors and up to 50 patients with *NRG1* gene fusion-positive solid tumors who have not received afatinib. Although the feasibility study did not identify this number of patients, further recruitment to non-responders to the survey invitation will be used to achieve the target number of patients planned for this study. Given the small number of patients targeted for study inclusion and anticipated differences in baseline characteristics between afatinib-treated and patients treated with other systemic therapies, statistical comparisons are not planned. In lieu of a comparative analysis between the afatinib-treated and non-afatinib treated patients are exploratory, the number of patients in each cohort and the precision of estimates are presented (**Table 4**). With up to 70 patients in the afatinib-treated cohort, the standard error (SE) of any bivariate response variable is expected to be between 5.5% and 11.7%.

Table 4. Precision of point estimates around number of patients.

Point Estimate of Proportion	Total Number of eCRFs				
	n=30 (SE)	n=50 (SE)	n=70 (SE)	n=100 (SE)	n=150 (SE)
5%	± 7.8%	± 6.0%	± 5.5%	± 4.3%	± 3.6%
20%	± 14.3%	± 11.1%	± 9.4%	± 7.8%	± 6.4%
30%	± 16.4%	± 12.7%	± 10.7%	± 9.0%	± 7.3%
40%	± 17.5%	± 13.6%	± 11.5%	± 9.6%	± 7.8%
50%	± 17.9%	± 13.9%	± 11.7%	± 9.8%	± 8.0%

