Data sources:	
De-identified, patient-level data will be obtained from providers in the [REDACTED] who will complete an eCRF for eligible patients. [REDACTED] will recruit providers from [REDACTED] to participate. [REDACTED] is a community of over 7,000 oncologists, hematologists and urologists from across the U.S., with varying levels of time in practice, from practices both within and outside of group purchasing organizations. A subset of this provider group (~800) participates in retrospective observational research studies. All provider participation in the study is voluntary.
 
Providers will abstract clinical and treatment related data as available from the patient's EHR from the time of diagnosis of their primary malignancy through the last date of follow-up with the patient or death. Providers will complete an eCRF for all eligible patients and will begin data abstraction with the first eligible patients, subsequently selecting consecutive patients moving forward. Required data elements are specified in the study inclusion/exclusion criteria; non-required data elements may be missing/unknown. Providers may abstract data into the eCRF for both patients they personally managed/treated or those managed/treated by other providers within their practice.
 
Providers are compensated for their time completing data abstraction into the eCRF only after subsequent data verification, as necessary. No source documents will be provided to [REDACTED] for verification; however, [REDACTED] will require duplicate data entry for a sample of patients' initial data collection to verify data point accuracy.

----------------------	--

Study size:

The total target number of patients is up to 120 patients, including up to 70 patients with an *NRG1* gene fusion-positive solid tumor treated with afatinib and up to 50 patients with an *NRG1* gene fusion-positive solid tumor who had not received afatinib at the time of data collection. The target number of patients was based on the results of a pilot feasibility study conducted by [REDACTED] with Boehringer Ingelheim (BI).

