In December 2019, [REDACTED] conducted outreach to approximately 800 providers in [REDACTED] to inquire as to the number of patients with *NRG1* gene fusion-positive solid tumors treated with afatinib whom they had personally managed or who were cared for at their practice. Providers were presented with similar inclusion criteria as those described above. In total, 12 oncologists completed short eCRFs describing a total of 108 patients. Of those, 67 (62%) were treated with afatinib and 41 (38%) had not received afatinib.

Based on the feasibility study, [REDACTED] will target up to 70 afatinib-treated patients with *NRG1* gene fusion-positive solid tumors and up to 50 patients with *NRG1* gene fusion-positive solid tumors who had not received afatinib. Although the feasibility study did not identify this number of patients, further recruitment of non-responders to the survey invitation will be used to achieve the target number of patients planned for this study. In lieu of a comparative analysis between the afatinib-treated and non-afatinib treated patients are exploratory, the precision of estimates involving 70 patients in the afatinib-treated cohort would be associated with a standard error of any bivariate response variable between 6.0% and 13.9%.

Data analysis:	
Demographic and clinical characteristics will be reported via descriptive analyses, including counts and frequencies for dichotomous and categorical variables, while measures of centrality (mean, median) and spread (min, max, standard deviation, interquartile range, as appropriate) will be used for continuous variables. These characteristics will be described at the time of initial diagnosis of advance/metastatic disease and at the time of initiation of each line of therapy received.
																						
	
For disease response, the point estimate for ORR and associated 95% confidence interval will be calculated for each cohort. The Kaplan-Meier method will be used to estimate any time to event outcome including DOR, DOCB, TOT, TTP, PFS, and OS to account for any right censoring (e.g., patient had not discontinued therapy, patient had not progressed or died).
																						

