9.7 DATA ANALYSIS

Demographic and clinical characteristics will be reported by descriptive analyses including counts and frequencies for dichotomous and categorical variables, while measures of centrality (mean, median) and spread (min, max, standard deviation, interquartile range, as appropriate) will be used for continuous variables. These characteristics will be described at the time of initial diagnosis of advanced/metastatic disease and at the time of initiation of each line of therapy received, for the afatinib cohort and separately for the other systemic therapy cohort. No statistical comparisons will be made across these two cohorts in terms of demographic, clinical characteristics, and clinical outcomes.

The calculations for all outcomes (e.g., ORR, DOR, DOCB, TOT, TTP, PFS, OS) are defined in **Table 2** in Section **9.3.2 Outcomes**. For disease response, the point estimate for ORR and associated 95% confidence interval (CI) will be calculated for initial response to index therapy (i.e., afatinib or other systemic therapy) and best response to index therapy, for each cohort. ORR will be reported among subgroups within each of the treatment cohorts, by tumor type and line of therapy. The Kaplan-Meier method will be used to estimate time-to-event outcomes (DOR, DOCB, TOT, TTP, PFS, and OS) to account for any right-censoring (e.g., patient had not discontinued therapy, patient had not progressed, or died). Time-to-event outcomes will be described for each of the two treatment cohorts and in subgroups within the two treatment cohorts, according to solid tumor and line of therapy. All study outcomes will be reported separately for those treated with afatinib monotherapy. In the event an outcome cannot be assessed for a given patient, that patient would be omitted from assessment of that outcome; reason for omission in a given outcome assessment will be reported.

Cumulative incidence, severity, and timing of AEs during the index therapy will be summarized and displayed in number/percentage form for each of the treatment cohorts, separately. All safety endpoints will be analyzed descriptively. AE reporting is summarized in Section **11 Management and Reporting of Adverse Events/Adverse Reactions**.

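### Section 9.5 and Table 4 call 95% half-widths standard errors, the abstract gives the 50-patient range for the 70-patient cohort, and two cells in the 5% row are wrong

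*Combined protocol and SAP*

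**What the plan says.** Section 9.5 plans no comparison between cohorts and offers the precision of single-cohort estimates instead. It introduces its figures with "With up to 70 patients in the afatinib-treated cohort" and then states that "the standard error (SE) of any bivariate response variable is expected to be between 5.5% and 11.7" percent. Table 4, titled "Precision of point estimates around number of patients", covers proportions of 5%, 20%, 30%, 40% and 50% at n=30, 50, 70, 100 and 150. Each column is headed SE and each entry carries a ± sign.

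The abstract (Section 4, Study size) refers to "the precision of estimates involving 70 patients in the afatinib-treated cohort" and gives a "standard error of any bivariate response variable between 6.0% and 13.9" percent.

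Neither place gives a confidence level or an interval method for these figures. The only confidence level in the plan is in the analysis of response, where "the point estimate for ORR and associated 95% confidence interval (CI) will be calculated" (Section 9.7).

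**The concern.** Two current sections give different precision for the same 70 patients. Both use a statistical term that cannot apply, since an SE of 11.7% for a proportion is impossible at n=70. Both also write bivariate where a binary variable is evidently meant.

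The study tests no hypothesis and makes no comparison, so this is the plan's only quantitative statement of what the sample can deliver. The milestones schedule the protocol for submission to the FDA, and Section 7 says the data may support label-expansion requests. Readers may therefore rely on the figures when judging how informative a single-cohort response rate will be.

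**Working it through.** **Inputs.** The cohort sizes are 70 and 50, and the proportions run from 5% to 50% (Section 9.5, Table 4). The confidence level is taken as two-sided 95%, z = 1.96. The plan does not state this for Table 4; it is inferred from the values and agrees with the 95% CI for ORR in Section 9.7.

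**Formulas.**
- Standard error: SE = sqrt(p(1−p)/n)
- Normal-approximation half-width: 1.96 × SE
- Wilson half-width, as an alternative: [z/(1+z²/n)] × sqrt(p(1−p)/n + z²/(4n²))

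**Step 1: which formula reproduces the table?** All 25 cells were recomputed and compared at one decimal.

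| Formula | Cells matched |
|---|---|
| SE | 0 of 25 |
| 1.96 × SE | 23 of 25 |
| Wilson half-width | 5 of 25 |

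The table is a table of 95% normal-approximation half-widths.

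**Step 2: the 70-patient cohort.**
- p=50%: SE = sqrt(0.25/70) = 5.98%. Half-width = 1.96 × 5.98 = 11.7%, as printed.
- p=5%: SE = sqrt(0.05 × 0.95/70) = 2.60%. Half-width = 1.96 × 2.60 = 5.1%. Printed: 5.5%.

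As p(1−p) peaks at p=50%, no proportion can have an SE above 5.98% at n=70. An SE of 11.7% at p=50% would need n = 0.25/0.117² = 18.3, about 18 patients.

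**Step 3: the abstract's range.**
- n=50, p=5%: SE = 3.08%, half-width 6.04%.
- n=50, p=50%: SE = 7.07%, half-width 13.86%.

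Rounded, these are the abstract's 6.0% and 13.9%, and they are the first and last entries of Table 4's n=50 column. Read as half-widths for 70 patients they are too wide by 6.0 − 5.1 = 0.9 points at p=5% and by 13.9 − 11.7 = 2.2 points at p=50%.

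**Step 4: the 5% row.**

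| n | Printed | 1.96 × SE | Wilson |
|---|---|---|---|
| 30 | 7.8 | 7.80 | 8.94 |
| 50 | 6.0 | 6.04 | 6.65 |
| 70 | 5.5 | 5.11 | 5.49 |
| 100 | 4.3 | 4.27 | 4.51 |
| 150 | 3.6 | 3.49 | 3.62 |

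The n=70 and n=150 cells do not follow the method of the other three, by 0.4 and 0.1 points. Both agree with Wilson, but Wilson misses the other three cells, so it is not the table's method. The documents do not show where the two values come from.

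Neither formula gives the Section 9.5 range of 5.5% to 11.7% at both ends. At n=70 the normal approximation gives 5.1% to 11.7% and Wilson gives 5.5% to 11.4%.

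**Step 5: effect of the label.** Treating 11.7% as an SE gives a 95% interval of ±1.96 × 11.7 = ±22.9 points, against the ±11.7 that the value already represents.

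**The case against.** The strongest case on the other side concerns weight. Nothing in the study rests on these figures: "The target number of patients was based on the results of a pilot feasibility study", the cohort sizes are upper quotas, no hypothesis is tested, and the ORR interval will be computed from the observed data. Every error makes the study look less precise than it is. The ± sign and the table title also point a careful reader towards half-widths. All of this stands and limits the severity, but it does not remove the error, because the prose spells out standard error in full and the abstract contradicts the body whichever reading is taken.

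A second objection is that the cell errors are small and that n=150 is not a planned size. That is fair for n=150. The n=70 cell matters more, because it supplies the lower bound quoted in Section 9.5 for the main cohort.

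A third is that the normal approximation behaves poorly at p=5%. The lower limit falls just below zero at n=70 (5.0 − 5.1 = −0.1) and further below at n=50 (5.0 − 6.0 = −1.0). That is true of the method, but 23 of the 25 cells already use it. Naming it makes the table honest about what it shows and does not commit the ORR analysis to it.

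**Conclusion.** The concern holds in all three parts. The figures labelled SE in Section 9.5 and Table 4 are, apart from the two stray cells, 1.96 times the standard error; the true SE at n=70 is 2.6% to 6.0%. The abstract attaches the n=50 range to the 70-patient cohort. By the table's own method, the p=5% cells should read 5.1% at n=70 and 3.5% at n=150, so the range for 70 patients is 5.1% to 11.7%.

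The contradiction between abstract and body, and the impossibility of an 11.7% SE at n=70, need no assumption about method. Reading the table as 95% normal-approximation half-widths is an inference from the 23 matching cells. This should be corrected because it is the plan's only precision statement, but it does not affect the validity of any planned result.

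**What to change.** 1. Relabel the Table 4 columns as 95% CI half-width (normal approximation).
2. Correct the p=5% cells to 5.1% (n=70) and 3.5% (n=150).
3. Use one sentence in both the abstract and Section 9.5, for example: *For a binary outcome with a proportion of 5% to 50%, the 95% CI half-width (normal approximation) is 5.1% to 11.7% with 70 patients (SE 2.6% to 6.0%) and 6.0% to 13.9% with 50 patients (SE 3.1% to 7.1%).*

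Keeping the SE label and printing true standard errors throughout would serve equally well, as would recomputing every cell by another named interval method. What matters is one stated method and the same figures in both sections.

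The cost is one table label, two cells and one sentence in two places. Enrolment, data collection and analysis do not change.

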9.6 DATA MANAGEMENT

The research team will be responsible for the programming, testing, and hosting of data from submitted eCRFs. Providers will access the eCRF through a secure web-based portal with all data stored on encrypted, password protected, and HIPAA-compliant servers housed within the [REDACTED] electronic data storage infrastructure. These processes and systems are vetted during the

field-testing procedures. The software used to program the eCRF is the Qualtrics Survey Software. A log of any modifications made to the underlying data as a result of quality control/quality assessment procedures will be maintained. An original copy of the submitted data will always also be maintained. The log will describe any changes made to the database by [REDACTED]

9.7 DATA ANALYSIS

Demographic and clinical characteristics will be reported by descriptive analyses including counts and frequencies for dichotomous and categorical variables, while measures of centrality (mean, median) and spread (min, max, standard deviation, interquartile range, as appropriate) will be used for continuous variables. These characteristics will be described at the time of initial diagnosis of advanced/metastatic disease and at the time of initiation of each line of therapy received, for the afatinib cohort and separately for the other systemic therapy cohort. No statistical comparisons will be made across these two cohorts in terms of demographic, clinical characteristics, and clinical outcomes.

The calculations for all outcomes (e.g., ORR, DOR, DOCB, TOT, TTP, PFS, OS) are defined in **Table 2** in Section **9.3.2 Outcomes**. For disease response, the point estimate for ORR and associated 95% confidence interval (CI) will be calculated for initial response to index therapy (i.e., afatinib or other systemic therapy) and best response to index therapy, for each cohort. ORR will be reported among subgroups within each of the treatment cohorts, by tumor type and line of therapy. The Kaplan-Meier method will be used to estimate time-to-event outcomes (DOR, DOCB, TOT, TTP, PFS, and OS) to account for any right-censoring (e.g., patient had not discontinued therapy, patient had not progressed, or died). Time-to-event outcomes will be described for each of the two treatment cohorts and in subgroups within the two treatment cohorts, according to solid tumor and line of therapy. All study outcomes will be reported separately for those treated with afatinib monotherapy. In the event an outcome cannot be assessed for a given patient, that patient would be omitted from assessment of that outcome; reason for omission in a given outcome assessment will be reported.

Cumulative incidence, severity, and timing of AEs during the index therapy will be summarized and displayed in number/percentage form for each of the treatment cohorts, separately. All safety endpoints will be analyzed descriptively. AE reporting is summarized in Section **11 Management and Reporting of Adverse Events/Adverse Reactions**.

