9. RESEARCH METHODS

9.1 STUDY DESIGN

This is a non-interventional, retrospective, US, multi-site, cohort study based on existing data from medical records of patients with *NRG1* gene fusion-positive solid tumors treated with afatinib or other systemic therapy. Two cohorts of patients will be identified. The first includes any patient with *NRG1* gene fusion-positive solid tumors who has received afatinib in any line of therapy (afatinib cohort) between 01/01/2017 and 03/31/2020. The second includes any patient with *NRG1* gene fusion-positive solid tumors who has not received afatinib in any line of therapy (other systemic therapy cohort) during the same period and no history of afatinib use. Follow-up will include at least 3 months after initiation of afatinib or other systemic therapy, unless a patient died prior to 3 months of follow-up.

In total, up to 120 patients with *NRG1* gene fusion-positive solid tumors will be selected for this study, of whom up to 70 will be afatinib-treated and up to 50 will be treated with other systemic therapy. Study objectives are to describe these patients and calculate the ORR in each group, as well as to estimate PFS, TOT, TTP, OS, DOR, and DOCB along with describing the incidence and severity of AEs among patients in the two cohorts. Data to be collect through this medical chart review include patient demographics, clinical characteristics at the time of diagnosis/initiation of a line of therapy, treatment-related data points (dates of initiation, discontinuation, dosing), AEs occurring during therapy, disease response, date of progression and/or death.

Given the small number of patients targeted for study inclusion and anticipated differences in baseline characteristics between afatinib-treated and patients treated with other systemic therapies, statistical comparisons are not planned. In lieu of statistical comparisons between cohorts, the non-afatinib arm will provide context for interpreting results among those treated with afatinib. Specifically, this context includes what patients with *NRG1* gene fusions not treated with afatinib look like, how they are managed and treated, and what their clinical outcomes look like. The non-afatinib arm will provide a broader understanding of *NRG1* gene fusions among patients with solid tumors

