9.2 SETTING

Approximately 20 or more unique providers will participate in this research study. To minimize potential bias, the maximum number of patients each provider may select and complete data abstraction for is capped at 30; for any provider who submits >10 patients, their data will be reviewed in detail by a clinician and analyst to identify any data quality issues (see Section **9.8.2 Data Validation** for further details on data quality assurance and control measures). Data

will be collected through an electronic case report form (eCRF) completed by the patients' providers who volunteer to participate in the study. Providers will be compensated at fair market value for the time to complete data abstraction and quality control procedures, which are estimated to take up to 1 hour per patient.

Recruitment of providers will be conducted electronically. Providers who responded to an initial feasibility request and reported treating potentially eligible patients will be contacted and invited to participate. Recruitment to fill the up-to-120-patient quota will run for 4 weeks from the date of recruitment launch. During that time, the per-cohort quotas will be electronically monitored to ensure that the final number of patients achieves up to 70 patients with *NRG1* gene fusion-positive solid tumors treated with afatinib and up to 50 with an *NRG1* gene fusion-positive solid tumor not treated with afatinib at the time of data collection. As recruitment for a cohort is completed, no further patient data entry will be allowed for that cohort; however, providers actively completing an eCRF at the time of quota close for a cohort will be allowed to complete that eCRF, and the total number of patients per cohort may exceed the quotas.

Providers will be asked to identify all eligible patients, and starting with the earliest index date, chronologically select consecutive patients meeting the eligibility criteria and complete the data abstraction. The eCRF is structured to allow data collection regarding patient clinical history at the time of initial diagnosis of their solid tumor, initiation of index therapy (including dates of dose starts, stops, and interruptions), response to therapy, dates of disease progression, AEs, (including dates of onset, recovery, and reported deaths).

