The ORR among patients with *NRG1* gene fusion-positive solid tumors treated with afatinib and among patients with *NRG1* gene fusion-positive solid tumors treated with other systemic therapy will be calculated as the proportion of patients with a complete response (CR) or partial response (PR) out of all patients (CR+PR/all patients) (see **Table 2** below). Disease response for determining the ORR will be reported as recorded in the patient's EHR, including the date of radiographic imaging used to substantiate the patient's initial and best response to therapy. Providers will indicate whether the patient experienced a CR, PR, stable disease (SD), or progressive disease (PD). No independent blinded review of radiology studies will be conducted. Lesion measurements at baseline (initiation of afatinib; initiation of other systemic therapy for non-afatinib treated patients), initial response, and best response will be abstracted as available. Changes in the number, locations, and sizes of lesions at initial and best response to therapy will be evaluated by [REDACTED] using RECIST v1.1 guidelines. The sum of lesion measurements will be assessed at baseline and at follow-up scans to calculate the percent change in sum of target lesions, as well as account for new lesions on follow-up scan in order to classify response by RECIST v1.1 criteria. Actual scan images will not be reviewed; the calculation of real-world disease response will be based on the lesion measurements provided. Other outcomes include PFS, TOT, TTP, OS, DOR, DOCB, AEs. Definitions of these outcomes are shown in **Table 2**.

Table 2. Study outcomes and definitions.

Outcome	Definition
ORR	Proportion of patients with a complete response (CR) or partial response (PR) out of all patients (CR+PR/all patients) at initial response assessment and best response
DOCB	Duration of clinical benefit (DOCB) will be calculated as the time from initial response (for any patient with a complete, partial, or stable disease response initially) until the earliest of either disease progression or death. Patients who discontinue therapy due to a reason other than progression will be censored on the date of discontinuation. Patients still on therapy at the time of data cut-off will be censored on their last visit date.

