9.12 BIAS

Provider and patient selection bias may exist in this study. Provider selection bias will be minimized by only allowing providers to contribute up to 30 patients each. It is expected, however, given the rarity of the patient profile included in this study, that the mean number of patients each provider will contribute is approximately 5 and the total number of providers participating will be greater than 20. Patient selection bias will be minimized to the extent possible by requesting providers complete eCRFs for eligible patients starting chronologically with the earliest patient meeting the criteria and selecting patients consecutively thereafter. To assess the degree of selection made by the participating provider, the total number of patients meeting the study selection criteria will be collected (e.g., 5 patients meet study inclusion/exclusion criteria) will be compared to the number of patients contributed to the study (e.g., 3 patients submitted as CRFs).

In addition, the extent of both provider and patient selection bias is likely minimized by the stringent study selection criteria. Because of the relative rarity of *NRG1* fusion-positive histology, the total prevalence of this patient population is likely small, minimizing potential selection biases.

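### Table 4, and by inference the ORR confidence interval, assume independent patients although several may come from one provider; if their responses are correlated, the intervals are likely too narrow

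*Combined protocol and SAP*

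**What the plan says.** **Analysis.** Section 9.7 states that "the point estimate for ORR and associated 95% confidence interval (CI) will be calculated for initial response to index therapy" and likewise for best response, by cohort. The interval method is not named. Time-to-event outcomes get Kaplan-Meier estimates, with no mention of confidence limits. Clustering, robust variance and provider-level sensitivity analyses do not appear.

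**Precision.** Section 9.5, Table 4, gives precision as a function of the proportion and the number of eCRFs only. The entries are labelled SE.

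**Who supplies the data.** Under section 9.2.1 the providers choose the patients. Under section 9.3.2 they enter the response category, and "No independent blinded review of radiology studies will be conducted". A RECIST v1.1 classification is also derived centrally, but from the lesion measurements that the providers enter.

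**Concentration.** In section 9.2, "the maximum number of patients each provider may select and complete data abstraction for is capped at 30", and anyone submitting more than 10 has their data reviewed in detail. "Approximately 20 or more unique providers will participate in this research study". Section 9.12 expects that "the mean number of patients each provider will contribute is approximately 5". For the pilot, section 9.5 reports: "In total, 12 oncologists completed short eCRFs describing a total of 108 patients".

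**The concern.** Patients abstracted by one provider share an abstractor, a practice and probably a case mix and reading habit. That is a plausible source of positive correlation in recorded response. An interval built for independent patients then claims more information than the data hold. The cap, the review above 10 patients and the outlier checks in section 9.8.2 are aimed at bias and data quality; none of them changes the variance.

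Concentration is realistic. The 12 pilot oncologists alone reported 67 afatinib patients against a target of 70. Section 9.2 invites the feasibility responders, limits recruitment to 4 weeks and closes entry once a quota fills. The afatinib cohort could therefore come largely from about a dozen providers.

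No between-cohort comparison is planned, so each cohort's ORR and its interval carry the efficacy message. Section 7 says that the data may support label-expansion applications. As planned, no output would show whether one provider drives the ORR.

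**Working it through.** **Inputs from the documents**
- Cohort sizes (9.1): "up to 70 will be afatinib-treated and up to 50 will be treated with other systemic therapy".
- Cap per provider (9.2): 30, both cohorts together.
- Expected mean per provider (9.12): about 5, so 120/5 = 24 providers and 70/24 = 2.9, about 3, afatinib patients each.
- Pilot (9.5): 108/12 = 9 patients per provider; 67/12 = 5.6 afatinib patients per provider. The afatinib share is 62% (Abstract, study size).

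**Assumed:** ICC from 0.02 to 0.10. The documents give no value.

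**Step 1: reproduce Table 4.** Half-width = 1.96 × √(p(1−p)/n). At p = 0.5 and n = 70 this is 1.96 × √(0.25/70) = 1.96 × 5.98% = 11.7%, as printed. The formula matches 23 of the 25 cells to 0.1 point. The exceptions are p = 5% at n = 70 (5.1% against 5.5%) and at n = 150 (3.5% against 3.6%); a Wilson half-width gives those two values but also assumes independence. So Table 4 contains no design effect, and its entries are 95% half-widths. The standard error at n = 70, p = 50% is 6.0%.

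**Step 2: allow for clustering.** Design effect DE = 1 + (m − 1) × ICC, where m = Σmᵢ²/Σmᵢ when provider contributions differ. Half-width = 11.7 × √DE. Actual coverage of the ordinary interval = 2Φ(1.96/√DE) − 1.

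Effective cluster sizes:
- Protocol expectation: m = 2.9.
- Pilot rate: m = 5.6, taking equal contributions. Unequal ones would raise it.
- One provider at the cap with the pilot split: 0.62 × 30 ≈ 19 afatinib patients, the other 51 over 19 providers. m = (19² + 51²/19)/70 = 7.1.
- Extreme: one provider with 30 afatinib patients, ten with 4. m = (900 + 160)/70 = 15.1.

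| Afatinib patients per provider (n = 70, p = 50%) | DE | Half-width, points | Coverage of ordinary 95% CI |
|---|---|---|---|
| Independent (Table 4) | 1 | 11.7 | 95% |
| About 3 each | 1.04 to 1.19 | 11.9 to 12.8 | 95% to 93% |
| 5.6 each | 1.09 to 1.46 | 12.2 to 14.2 | 94% to 90% |
| One with 19, 51 over 19 others | 1.12 to 1.61 | 12.4 to 14.9 | 94% to 88% |
| One with 30, ten with 4 | 1.28 to 2.41 | 13.3 to 18.2 | 92% to 79% |

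The ranges run from ICC 0.02 to 0.10. The 14.2 uses m rounded to 5.6; 67/12 unrounded gives 14.1. With ICC = 0 every row stays at 11.7.

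**The case against.** **The narrowing is conditional.** It needs a positive ICC, and the documents give none. Section 9.7 names no interval method, so the independence of the planned ORR interval is inferred from its silence and from Table 4. Both points stand.

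**At the protocol's expected spread the effect is small.** At about 3 afatinib patients per provider the half-width grows by 0.2 to 1.1 points, in a descriptive study with no hypothesis test. This stands too, but the pilot average of 9 per provider is well above the expected 5.

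**The extreme case should not be read as the likely one.** A reader might infer from the cap that one provider will supply 30 of the 70 afatinib patients (43%) and that coverage falls to 79%. The cap is a maximum that spans both cohorts, so this needs a provider to fill it entirely with afatinib patients. At the pilot split the contribution is about 19.

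**A shared assessor is not established.** A reader might infer that each provider treats and scores all of his or her patients. Section 9.4 allows abstraction of patients managed by colleagues in the practice, and section 9.3.2 takes response as recorded in the EHR beside the centrally derived RECIST class. The practice may be the better cluster. The abstractor and the source of the lesion measurements are still shared.

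**Table 4 calls its entries SE.** Read literally, 11.7% exceeds even the extreme clustered standard error, √(0.25 × 2.41/70) = 9.3%. The table understates uncertainty only when its entries are read as the half-widths they are.

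**Provider concentration is partly handled.** The cap, the review above 10 patients, the outlier analysis and the comparison of eligible with submitted patients (9.12) are useful, but none of them widens an interval or shows a provider's influence on the ORR.

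**Conclusion.** The point holds in conditional form. Table 4 assumes independent patients, and nothing in section 9.7 suggests that the ORR interval will do otherwise. If responses within a provider are positively correlated, both are likely too narrow. With an assumed ICC of 0.02 to 0.10, the plausible range at n = 70 and 50% runs from almost no change (11.9 points) to about 14 or 15 points against 11.7. It reaches 18.2 only in the extreme allocation. The documents do not support saying outright that the intervals are too narrow, or by how much. The ORR estimate remains usable. This is a low-cost improvement, worth making because the pilot was concentrated in few providers and the ORR stands without a comparison.

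**What to change.** In section 9.7:
- Name the ordinary ORR interval method and keep that interval as the main one.
- Add as a sensitivity analysis a provider-clustered interval, for example a Wilson interval adjusted by the design effect. Use the practice as the cluster where several providers share one.
- Report the distribution of patients per provider in each cohort.
- Give a leave-one-provider-out ORR for every provider supplying more than 10 patients, the group that section 9.2 already singles out. This is informative whatever the ICC.
- If Kaplan-Meier confidence limits are reported, treat them the same way.

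Under Table 4, and where its range is quoted in the text, state that the entries are 95% half-widths assuming independent patients, not standard errors.

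The cost is a few lines of text and code. Provider identity must already be held to apply the cap, the review above 10 patients and the per-provider validation; a practice code may have to be added to the eCRF. The secondary intervals will be somewhat wider, and cluster methods are approximate with about 12 to 24 unequal clusters, which is why the ordinary interval should stay beside them.
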